The program will center on establishing health-related goals such as increasing consumption of fruits and vegetables, increasing physical activity time, decreasing hours spent in front of a screen, and reducing consumption of sweetened beverages. The program also will include the use of self-monitoring and positive reinforcement.

Physical activity sessions: Classes will be implemented 3 days a week for 30 minutes each. Children will work on developing different skills such as: flexibility, strength, elasticity and resistance. The Zoom digital platform will be used for the online (live) sessions. The classes will be recorded, in case the children want to do a class later.

Parent's participation: Parents who agree to participate in the program will be given a user to access a web page (www.salud-nutricional.com), where children's activities will be uploaded. This will be used to upload nutrition information, parenting activities, and study questionnaires. A private Facebook group will be created to upload teaching material (videos, infographics, messages and images) on a weekly basis. The difference between using the website and Facebook is that on the page the participants will be able to have the information ordered, upload their activities and study questionnaires. The topics addressed each week will be the same as those seen with the children in the nutrition sessions. On Facebook, they will have spaces for comments, questions, feedback and social support.

Control group: The control group will receive general nutrition recommendations at the beginning of the program, based on the Nutrition and Physical Activity Guidelines in the Context of Overweight and Obesity in Mexican Population.²⁴ A digital brochure will be sent in online format to the mail or through the WhatsApp application to parents. Upon completion of the study, they will be offered access to the materials from all the onlie lifestyle sessions, as well as physical activity videos for children recorded by the physical activity team.

Outcomes

The primary outcome is the change of the BMI Z-score from baseline to 4 months between the intervention group and the control group. The change in BMI Z-score for each individual will be obtained by subtracting the BMI Z-score value at 4 months minus the baseline value. The difference between groups will be obtained by subtracting the mean of the change in the intervention group minus that of the control.

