Study measurements will be performed at baseline and at 4 months. The primary outcome (BMI Z-score), waist circumference and triceps skinfold, will be measured by a person blinded to the allocation group and trained in the measurement of these variables. These anthropometric measurements will be carried out at the participants' homes in an outdoor area. Hygiene measures and recommendations will be followed to reduce the risks of contagion (use of NK95 face masks, plastic face shield, surgical suit, gloves, etc. short exposure time and disinfection of materials). Measurements will be made in less than 15 minutes. Before the home visit, a questionnaire will be sent to screen for possible symptoms related to COVID-19. Lifestyle questionnaires will be conducted online.

Primary outcome

- **BMI Z-score:** The measurement will be obtained using the sex, age, weight (kg) and height (m) of the participants. The height and weight will be combined (kg/m²) to obtain the BMI Z-score, expressed in units of standard deviation. Using The WHO Anthro Plus software.²⁵

Secondary outcomes

- **Weight:** To obtain the weight (kg), a TANITA SC-240 will be used. The measurement will be used to obtain the BMI Z-score.²⁶

- **Height:** The SECA 213 stadiometer will be used, following the Frankfurt plan. This measure will be used to obtain the BMI Z-score.²⁶
- **Waist circumference:** A Lufkin metallic anthropometric tape will be used. The umbilical scar will be taken as reference.²⁶
- **Body fat:** It will be estimated with the measurement of the tricipital skinfold, using a formula validated for Mexican children. To take the tricipital skinfold, the ISAK methodology will be followed.^{27,28}
- **Relative fat mass:** This is an estimator of total body fat. A formula carried out with children (8-14 years) will be used where the data of waist circumference (cm), height and sex (0 boys and 1 girls) will be needed.²⁹
- **Nutrition knowledge:** A questionnaire designed by the study team will be used to assess knowledge on nutrition. It consists of 32 questions on nutrition and health.

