- **Food consumption:** Some questions from the semi-quantitative food frequency questionnaire from the National Health and Nutrition Survey were used.³⁰ We asked about the frequency of consumption of ultra-processed foods (sweet beverages, fried foods, cakes and cookies) and healthy foods (fruits, vegetables and water) in the previous 7 days. For each food, the size of the portion consumed was asked, considering an average portion established in the FFQ.
- **Physical activity and sedentary activities:** The physical activity and sedentary lifestyle part of the questionnaire “The Health Behavior in School-aged Children” (HBSC) was used, which is a validated lifestyle questionnaire for school-age children.³¹ It consists of 9 questions, 5 questions related to the time and frequency of physical activity and 4 to sedentary activities.
- **Nutrition knowledge:** a questionnaire designed by the research team (not validated) was used to assess the knowledge on nutrition and health. It consists of 32 questions with multiple choice answers. The results were evaluated on a scale from 0 to 10, the more correct answers, the greater score.

- **Quality of life:** The PedsQL™ (Pediatric Quality of Life Inventory) questionnaire was used, which was designed to assess quality of life aspects in both healthy pediatric patients (2 to 18 years old) and those with chronic diseases. The questionnaire consists of 23 questions about physical, emotional, social and school functioning. The responses are on a 5-point likert scale (never = 0 to always = 4). The score for each item is reversed and transformed to a linear scale of 0–100, with a higher score indicating a better quality of life.³²
- **Retention:** It will be evaluated with the percentage of participants (intervention and control group) who complete the intervention and the measurements at 4 months.
- **Participation or attendance of schoolchildren:** It will be evaluated with the percentage of attended intervention sessions and with the percentage of participants who attended all sessions.
- **Parent's participation:** At the end of the study, parents will be asked through an online questionnaire, the number of materials consulted from the program and will be reported as a percentage.
- **Acceptance.** Acceptability will be obtained with a questionnaire applied to children and parents to qualify the intervention, materials and benefits obtained with the intervention.

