- **Personal information.** The first step for the screening of the participants consists of an online questionnaire of personal data. This will be sent at the time of the invitation to the program. Personal data of the child, internet access and electronic device, if they have a disease, if they take medications or perform extra interventions that may affect body weight will be asked. In addition, the email and education leve lof the parents will be asked.

Withdrawal of participants

Participants may withdraw from the study at any time they wish, being able to inform the reason or not.

Statistical Analysis

The normality of the data will be evaluated with the Shapiro Wilk test. Data will be presented as mean and standard deviation (mean \pm SD) or median and interquartile ranges according to their distribution. An independent samples t-test or Mann-Whitney U test will be used to analyze the difference in BMI Z-score and changes in secondary outcomes between groups. A chi-square test will be used to make comparisons on categorical variables. Two-tailed tests with $p \leq 0.05$ will be used as the criterion for statistical significance.

Data will be analyzed with an intention-to-treat analysis. If participants decide to withdraw from the intervention, they will be asked if the measurement at 4 months can be obtained to have at least the primary outcome for inclusion in the intention-to-treat analysis. If data is not obtained for any reason or subjects were excluded due to a protocol violation, they will be replaced by their baseline measurement.

Results will focus on change in the primary study variable (BMI Z-score), while changes in secondary variables and sub-analyses (sex and BMI: normal, overweight/obese) will be considered exploratory only. For data analysis, NCSS version 10 software (Number Cruncher Statistical System for Windows, Kaysville, UT, USA) will be used.

Confidentiality

Identifiable information and will be kept confidential. Each participant will be assigned a code, therefore, their identifiable information will appear with that code and not with names. Only the physical files will keep the names, which will be kept by the principal investigator of the study, in a safe place. Only the study team may have access to the database, for their purposes.

Declaration of interest

The authors did not report any potential conflicts of interest.

REFERENCES

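### Baseline substitution enters missing 4-month values, and as worded even measured values of protocol violators, as zero change in the primary analysis

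*Combined protocol and SAP*

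**What the plan says.** All references are to the combined protocol and SAP.

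- **Statistical Analysis, second paragraph.** The principle is "Data will be analyzed with an intention-to-treat analysis". For children who withdraw from the intervention, "they will be asked if the measurement at 4 months can be obtained to have at least the primary outcome". The rule for everything else is "If data is not obtained for any reason or subjects were excluded due to a protocol violation, they will be replaced by their baseline measurement".
- **Outcomes.** "The change in BMI Z-score for each individual will be obtained by subtracting the BMI Z-score value at 4 months minus the baseline value". The arms are then compared on mean change, with a t-test or Mann-Whitney test at two-sided 0.05.
- **Statistical Analysis, third paragraph.** BMI Z-score change is the focus, while "changes in secondary variables and sub-analyses (sex and BMI: normal, overweight/obese) will be considered exploratory only".
- **Secondary outcomes, Retention.** This is the "percentage of participants (intervention and control group) who complete the intervention and the measurements at 4 months".

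The plan has no second missing-data method, no sensitivity analysis, no expected loss and no definition of a protocol violation.

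**The concern.** Put the substitution rule beside the definition of the outcome: baseline minus baseline is zero. (If weight and height were carried forward and the Z-score recomputed at the later age, it would be near zero.) The t-test or Mann-Whitney test then treats that zero as if it had been measured. The Introduction argues that children out of school gain more weight, so no change is not an obviously neutral value here.

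There are two separate problems. First, the substituted zeros can shrink a real difference, or create one where none exists if the arms lose different numbers. Second, the violation condition is joined to the missing-data condition by an *or*. A withdrawn child who is measured keeps the real value, but a measured child excluded for a violation may have it replaced. That removes observed post-randomisation data for a reason that may be related to treatment.

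This affects the only comparison that the plan does not call exploratory. Retention combines completing the intervention with being measured, so it would not tell a reader how many values were replaced in each arm.

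**Working it through.** **Inputs from the documents.** Total 50 to 70 children, 1:1, so 25 to 35 per arm; two-sided 0.05; outcome as defined above. The sample size was set by logistics, so there is no plan figure to reproduce.

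**Assumptions (not in the documents).** 30 per arm; SD of change 0.3 (0.2 and 0.4 also tried); common drift of +0.1 or +0.2 Z; losses as shown, random within arm. Results are from 40,000 simulated trials per scenario with a t-test, unless stated. The simulation error near 5% is sqrt(0.05 × 0.95 / 40,000) = 0.11 percentage points.

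**Bias.** Let d be the share replaced and m the mean true change of the replaced children, with subscript 1 for intervention and 0 for control. Then

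bias = d0·m0 − d1·m1.

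It is zero when the two products are equal, for example if the replaced children truly did not change. Equal random loss d multiplies a real difference by (1 − d). A check with loss related to outcome: 6 versus 3 lost, lost children at +0.3 and the others at +0.1. The truth is (0.8×0.1 + 0.2×0.3) − (0.9×0.1 + 0.1×0.3) = +0.02. The plan gives 0.8×0.1 − 0.9×0.1 = −0.01. The bias is −0.03 = 0.1×0.3 − 0.2×0.3.

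**No true effect, unequal loss.**

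| Lost (intervention vs control) | Drift | Formula | Simulated bias | Type I error |
|---|---|---|---|---|
| 3 vs 1 | +0.1 | (1/30 − 3/30)×0.1 = −0.0067 | −0.0068 | 4.8% |
| 3 vs 1 | +0.2 | −0.0133 | −0.0135 | 5.1% |
| 6 vs 3 | +0.1 | −0.010 | −0.0097 | 5.1% |
| 6 vs 3 | +0.2 | −0.020 | −0.0201 | 5.1% |
| 9 vs 3 | +0.1 | −0.020 | −0.0203 | 5.8% |
| 9 vs 3 | +0.2 | −0.040 | −0.0398 | 7.7% |
| 3 vs 9 | +0.1 | +0.020 | +0.0198 | 5.6% |
| 3 vs 9 | +0.2 | +0.040 | +0.0403 | 7.8% |

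For 9 vs 3 at drift +0.1, type I error is 6.6% with SD 0.2 and 5.2% with SD 0.4.

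**True difference −0.20 (means −0.10 and +0.10), equal loss.**

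| Lost per arm | Estimate, −0.20×(1 − d) | 95% interval coverage |
|---|---|---|
| 1 | −0.19 | 0.95 |
| 3 | −0.18 | 0.94 |
| 6 | −0.16 | 0.91 |
| 9 | −0.14 | 0.85 |

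At 6 per arm, coverage is 0.87 with SD 0.2 and 0.93 with SD 0.4.

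**Precision at 6 lost per arm.** The variance of the completed changes is (1 − d)·SD² + d(1 − d)·m² = 0.8×0.09 + 0.16×0.01 = 0.0736, so the SE is sqrt(2×0.0736/30) = 0.070. Full follow-up of all 60 children would give 0.3×sqrt(2/30) = 0.077. Losing data therefore appears to improve precision. The SD is sqrt(0.0736) = 0.27 instead of 0.30. Used to plan the definitive trial at a fixed target difference, it would understate the required size by 1 − 0.0736/0.09 = 18%.

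**Measured violators overwritten, intervention arm only, no effect, drift +0.1.** The bias is −(k/30)×0.1. For k = 1, 2, 3, 6 it is −0.003, −0.007, −0.010, −0.020, with type I error 5.1%, 4.9%, 5.2%, 5.8%. With k = 6 and drift +0.2, the formula gives −0.040 and the type I error is 8.2%.

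**Choice of test.** The plan says "The normality of the data will be evaluated with the Shapiro Wilk test" but does not say how the result selects the test. Suppose it is run per arm on the completed changes, and rejection in either arm leads to Mann-Whitney (4,000 trials). With 9 vs 3 lost, normality is rejected in 58% to 69% of trials, against 9% to 10% on observed values. Overall type I error stays at 5.8% and 8.3% for drift +0.1 and +0.2, so the Mann-Whitney route does not remove the problem.

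**The case against.** **Loss may be small.** Withdrawn children are asked for the measurement, it is taken at home, and "Measurements will be made in less than 15 minutes". At 3 vs 1 or 6 vs 3 lost, type I error is about 5%. Visible inflation needs something like 30% versus 10% loss plus a common drift, and nothing in the documents shows that this will happen. This stands as a limit on the size of the problem. But no expected loss is stated, and no planned analysis would reveal the effect if loss were larger.

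**The clause may mean something milder.** It may cover only removed children who have no 4-month value, and so be meant to keep them in the analysis. The Exclusion criteria list withdrawal of consent, which fits that reading. It is plausible, but the text does not say it. One to three overwritten children would hardly move the error rate, so this part is mainly a contradiction in wording.

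**The rule is conservative.** This is so for equal random loss, where power matches the observed-case t-test (61.6% each at 6 lost per arm). It is not so for unequal loss, which can favour either arm.

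**Observed-value analysis is not always better.** This is correct. With 9 vs 3 lost, completers at −0.10 and +0.10, and lost children truly unchanged, the truth is 0.7×(−0.10) − 0.9×0.10 = −0.16. The plan gives −0.16 and observed cases give −0.20. This is a reason for sensitivity analyses, not for a single untested rule.

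**Regression goes beyond the defect.** In part this stands. The planned test on observed values would cure the overwriting and the false zeros, but it needs loss to be unrelated to outcome within each arm. Regression allows loss to depend on the baseline covariates as well.

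**Conclusion.** The concern holds and should be corrected before the analysis. Two parts follow from the text alone: replaced children count as zero (or nearly zero) change, and the violation clause as worded contradicts intention to treat. The numerical size rests on assumed SD, drift and loss. It is negligible with a few children lost. With 20% to 30% equal loss, coverage falls to 0.91 to 0.85 for a true difference of −0.20. With 9 vs 3 lost and no effect, type I error is about 6% to 8%. The direction is not fixed in advance. The plan contains nothing that would let a reader see how far the result depends on the rule.

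**What to change.** 1. Delete the protocol-violation clause. Analyse every observed 4-month value in the arm to which the child was randomised, including violators and withdrawn children who are measured.
2. Name one primary method under a stated missing-at-random assumption: a linear model of the 4-month Z-score on arm, baseline Z-score, sex and age, using all observed values. Baseline Z-score and sex are the stratification factors in the Randomization section; age is in the same allocation database.
3. Keep baseline substitution as a labelled sensitivity analysis, and add one that imputes missing intervention children from the control-arm change. Both are needed:
   - If lost children revert to control-like change (9 vs 3 lost, control drift +0.1, intervention completers at 0), the truth is 0.3×0.1 − 0.1 = −0.07. The linear model gives −0.10, control-based imputation −0.07, and the plan 0 − 0.9×0.1 = −0.09. The plan would give −0.07 at drift 0 and −0.11 at drift +0.2.
   - If lost children keep the benefit (true −0.20, 6 lost per arm), the linear model gives −0.20 and the other two give −0.16.
4. Report the numbers missing and the numbers of protocol violators by arm. Take any SD for the definitive trial from observed values.
5. The document is dated 10/06/2021 and the programme ran from March to July 2021. If outcome data are already unblinded, label the change post hoc and report both analyses.

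**Cost.** SAP wording and ordinary regression, with no extra children or visits. The interval is wider: at 20% loss the SE is 0.086 (observed-case t-test) to 0.089 (linear model with covariates that explain almost none of the change), instead of 0.070. Power at a true −0.20 is unchanged for the observed-case t-test (61.6%). For that linear model it is 59.0% against 61.4% under the plan, about 2 points lower.

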Children from a public elementary school in Hermosillo, Sonora will be invited to participate in the study. It is worth mentioning that this public school is not representative of all the schools in Hermosillo, Sonora. Hermosillo is a city of about 884,273 inhabitants and around of 392 public elementary schools. It is located in the state of Sonora, in northwestern Mexico. Because the program is entirely online, students who agree to participate will take the intervention from home.

Sample size

No studies of online lifestyle interventions to prevent obesity in schoolchildren during the pandemic were found to obtain the effect size and standard deviation needed to estimate the study sample size. So, we decided that it would be a pilot study of at least 50 participants and no more than 70. This was decided considering our logistical capacity, which implies measuring the response variables at home in a period of 2 weeks, in addition to being able to provide intervention, among other things. The invitation will be made to all students from fourth to sixth grade of a public school in Hermosillo Sonora.

Eligibility criteria

Sign the consent and informed assent and complete the anthropometric measurements and lifestyle questionnaires.

Inclusion criteria

- 4th, 5th and 6th grade students from the participating elementary school.
- Have access to the internet.
- Have an electronic device (eg computer, laptop, tablet or smartphone).
- Nutritional status: normal weight, overweight or obesity.

Exclusion criteria

- Have a medical condition that affects body weight.
- Taking medication that affects body weight.
- Take another intervention that affects body weight.
- Have a condition that prevents physical activity.
- Withdraw informed consent or assent.
- Have a sibling participating in the study.

Implementers

The lifestyle intervention will be implemented by a Nutritionist and two interns from the Bachelor's Degree in Physical Culture and Sports from the study team. In

addition, there will be the support of interns from the Nutritional Sciences Bachelor of the University of Sonora.

Interventions of the study

Online lifestyle intervention

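### Exclusion for a protocol violation triggers baseline replacement in its own right, so a measured 4-month BMI Z-score can be overwritten despite the stated intention-to-treat analysis

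*Combined protocol and SAP*

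**What the plan says.** All the key text is in the Statistical Analysis section of the combined protocol and SAP.

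- The principle: "Data will be analyzed with an intention-to-treat analysis".
- For children who withdraw from the intervention: "they will be asked if the measurement at 4 months can be obtained to have at least the primary outcome", so that a real value enters that analysis.
- The next sentence is the replacement rule: if "data is not obtained for any reason or subjects were excluded due to a protocol violation, they will be replaced by their baseline measurement".

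Four other places bear on it.

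- Outcomes defines the primary endpoint as the 4-month BMI Z-score minus the baseline value.
- Outcome measures plans both assessments without exception: "Study measurements will be performed at baseline and at 4 months".
- Under participation or attendance, session attendance is itself an outcome: "It will be evaluated with the percentage of attended intervention sessions".
- The exclusion criteria include one that can arise after randomisation: "Withdraw informed consent or assent".

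The documents do not define a protocol violation. They do not say who decides on exclusion or when, and no sentence keeps the observed 4-month value of an excluded child.

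**The concern.** The replacement rule has two triggers joined by 'or'. The first, data not obtained for whatever reason, covers all missing values. The second, exclusion for a violation, can add something only when a value exists. Read as written, the excluded child stays in the denominator of the assigned arm, but the measured change is discarded and replaced by 0.

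Intention-to-treat requires the outcome that occurred, in the assigned arm, whatever the adherence. The rule keeps the headcount and drops the outcome. It also gives an odd ordering: a child who leaves the intervention has the real value sought, while a child excluded for a violation can have a real value thrown away.

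The decision falls after allocation, on an undefined criterion, and acts on the primary outcome. The measurer of the anthropometric outcomes is blinded, but nothing says that whoever decides on exclusions is. Similar overwriting in both arms dilutes a true effect. Uneven overwriting can create or hide a difference, depending on which arm is affected and whether those children gained or lost.

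**Working it through.** **The text.** Change = 4-month value - baseline. If the 4-month value is replaced by baseline, change = baseline - baseline = 0.

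| Child | Trigger 1 (not obtained) | Trigger 2 (excluded for violation) | Does trigger 2 alter the result? |
|---|---|---|---|
| 4-month value missing, excluded | applies | applies | No, already replaced |
| 4-month value measured, excluded | does not apply | applies | Yes, measured change becomes 0 |

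**Inputs from the documents.** 50 to 70 children (Sample size) allocated 1:1 (Study design), so 25 to 35 per arm; two-sided 0.05 and a t-test or Mann-Whitney test (Statistical Analysis). One child is 1/35 = 2.9% to 1/25 = 4.0% of an arm. The plan has no effect size, SD or violation rate, so it has no figure of its own to reproduce.

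**Assumptions.** Overwritten shares vI and vC; mean changes mI and mC; SD of change 0.3, with 0.2 to 0.4 as a range. Except in the last case below, overwritten children have their arm's mean change.

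**Formula.** Difference after overwriting = (1 - vI)·mI - (1 - vC)·mC.

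| Case | vI, vC | mI, mC | True difference | After overwriting |
|---|---|---|---|---|
| A, both arms 10% | 0.1, 0.1 | 0, 0.2 | -0.20 | 0.9·0 - 0.9·0.2 = -0.18 |
| A, both arms 20% | 0.2, 0.2 | 0, 0.2 | -0.20 | 0.8·0 - 0.8·0.2 = -0.16 |
| B, intervention only | 0.2, 0 | 0.2, 0.2 | 0 | 0.16 - 0.20 = -0.04 |
| C, control only | 0, 0.2 | 0.2, 0.2 | 0 | 0.20 - 0.16 = +0.04 |
| D, intervention only | 0.2, 0 | -0.2, 0 | -0.20 | 0.8·(-0.2) - 0 = -0.16 |

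**Violators who differ from the rest.** Suppose 20% of the intervention arm are violators with mean change +0.20 and the others have -0.20. The true arm mean is 0.8·(-0.20) + 0.2·0.20 = -0.12. After overwriting it is 0.8·(-0.20) + 0.2·0 = -0.16, which flatters the intervention.

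**Scale.** The standard error of the difference is SD·√(2/n). At SD 0.3 it is 0.085 (n = 25) and 0.072 (n = 35). Over SD 0.2 to 0.4 it runs from 0.048 to 0.113. Every shift above is at most 0.04, below one standard error.

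**Simulation.** 200,000 trials per case, normal changes, SD 0.3, two-sample t-test at 0.05, with 5 of 25 or 7 of 35 children (20%) overwritten in each affected arm.

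| Quantity | 25 per arm | 35 per arm |
|---|---|---|
| Power at -0.20, nothing overwritten | 0.64 | 0.79 |
| Power at -0.20, 20% of each arm overwritten (A) | 0.53 | 0.68 |
| Type I error, B | 0.073 | 0.086 |
| Type I error, C | 0.075 | 0.087 |
| Type I error, as B with a gain of 0.10 z | 0.056 | 0.059 |
| As B (gain 0.20 z), 1 child overwritten | 0.05 | 0.05 |
| As B (gain 0.20 z), 3 children overwritten | 0.058 | 0.055 |

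**The case against.** The strongest reply is that overwriting is inferred. The sentence never says that a measured value will be discarded. The text is loosely edited (nutrition knowledge is listed twice as an outcome), so the second trigger may simply be redundant: two ways to end up without a usable 4-month value, offered as the fallback to the preceding sentence. On that reading nothing observed is lost, and the clause seems meant to keep violators in the analysis.

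This reading is possible, and the documents do not settle the matter. It does not rescue the plan. It means that follow-up of randomised children stops at exclusion, so values that could be obtained are never sought. That also departs from intention-to-treat and sits badly beside the effort made for children who withdraw. It is fair that the preceding sentence concerns withdrawal only, so this is a difference in treatment and not a strict contradiction. It is also fair that every child stays in the denominator: the fault is in the outcome value used, not in who is analysed.

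The second reply is about weight, and much of it stands. Eligibility is checked before randomisation. Attendance is an outcome, so missed classes should not be assumed to be violations. Nothing suggests that exclusions will be common. With one or two children overwritten, type I error barely moves. This is also a pilot sized on logistics, with no planned power to lose. These points limit the size of the problem. They do not make the rule right.

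**Conclusion.** The concern holds. As written, the rule can put an artificial zero change into the primary outcome in place of a measured one, contrary to the analysis principle stated in the same section. That the wording permits this is clear; whether the authors intended it is not.

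The likely effect is modest. Under the assumed values, 10% to 20% overwritten in both arms takes a true -0.20 z to between -0.18 and -0.16. Overwriting 20% of one arm shifts the difference by 0.04 z in either direction, with type I error up to about 0.09. These sizes rest on assumed violation rates, gains and SD, and on frequent exclusions. It should be fixed because the rule is wrong in principle, depends on an undefined judgement made after allocation, and is easy to correct. Whether baseline replacement suits values that are truly missing is a separate question.

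**What to change.** In Statistical Analysis, delete the second trigger (exclusion for a protocol violation) from the replacement sentence and add text such as:

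> We will try to measure every randomised child at 4 months unless consent or assent has been withdrawn. Each observed value will be analysed in the arm to which the child was assigned, irrespective of protocol violations or attendance. Imputation will be used only where the 4-month value is truly missing.

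If an analysis without violators is wanted, label it a per-protocol sensitivity analysis and define a protocol violation before outcome data are examined. Report the number of violations by arm. The first change corrects the defect; these last steps are good practice that makes it auditable.

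**Cost.** A sentence or two of text. If excluded children would not otherwise have been visited, 10% of 50 to 70 children is 5 to 7 extra home visits and 20% is 10 to 14 (assumed rates), each under 15 minutes according to Outcome measures. The Sample size section already set the limit of 70 by the capacity for "measuring the response variables at home in a period of 2 weeks", so these visits fall within the planned total.
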